1.3. STUDY OBJECTIVES

1.3.1. Primary Objectives:

The primary objectives were specifically chosen to meet the CHMP request to assess appropriate use of RPV-containing products. For all primary objectives, frequency and rates will be reported separately for the RPV and EFV-treated groups.

- To describe the proportion of patients treated with RPV-containing products in accordance with the SmPC. The proportion of patients treated with RPV in accordance with the SmPC will be described by estimating a proportion separately for each recommendation of patient treatment. The denominator for each proportion will consist of the number of all patients initiating RPV-containing regimens included in the study. Proportions will be estimated separately using the following numerators:
 - The number of patients naïve to HIV treatment regimens
 - The number of patients with documented pre-treatment screening for ARV RAMs
 - \circ The number of patients initiating RPV-containing regimens with a baseline viral load \leq 100,000 HIV-1 ribonucleic acid (RNA) copies/mL
- To describe treatment emergent RAMs in patients treated with RPV or EFVcontaining regimens
- To describe virologic failure in patients treated with RPV or EFV-containing regimens

The primary objective of the nested case-control analysis is to quantify separately the risk of virologic failure associated with ARV treatment adherence and pill intake with food.

1.3.2. Secondary Objectives:

The secondary objectives were specifically chosen to assist in meeting the CHMP request to assess appropriate treatment of patients with RPV-containing products in accordance with the SmPC or to provide context to events observed within the RPV-treatment group. For all secondary objectives, frequency and rates will be reported separately for the RPV and EFV-treated groups, as well as for RPV relative to EFV.

• To describe the demographic characteristics, comorbidities, and medical condition of patients initiating RPV or EFV treatment

- To describe antiretroviral (ARV) treatment status (naïve/experienced) of patients prior to initiating RPV or EFV treatment
- To describe prior use of ARV treatment, if any, of patients initiating RPV or EFV-containing regimens
- To describe the frequency of pre-treatment RAMs for RPV and EFV among patients subsequently initiating RPV or EFV treatment respectively
- To describe viral load at start of RPV or EFV treatment
- To describe viral load over the course of RPV or EFV treatment
- To describe HIV-treatment regimens and concomitant medications of patients initiating RPV or EFV-containing regimens
- To describe changes in HIV treatment and concomitant medication over the course of RPV and EFV treatment
- To describe reasons for switch of ARV treatment
- To describe adverse events over the course of RPV or EFV treatment

2. OVERVIEW OF STUDY DESIGN

2.1. Study Design

This DUS will be implemented in one or more large HIV cohorts established in Europe. Data will be collected longitudinally and recorded in the HIV cohorts' databases. A minimum of six hundred patients will be entered into the study based on the prescribing of RPV-containing regimens, either as a single agent or as a FDC. An additional minimal number of 600 patients will be entered into the study based on the prescribing of EFV-containing regimens. Retrospective data available in the HIV cohorts will be used to describe patient clinical characteristics prior to receipt of RPV-containing regimens.

Data will be collected in an observational manner such that the management of the patient is determined by the patient and the caregiver and not influenced by the DUS protocol. The DUS will evaluate care as it is provided. It will capture data on a heterogeneous population treated with RPV-containing regimens or EFV-containing regimens in a comprehensive manner without exclusions to assure representativeness of the populations treated with RPV or EFV-containing regimens.

All patients initiating RPV treatment will be eligible for inclusion in the DUS. Patients initiating EFV treatment will also be eligible for inclusion in the comparator group based on the date of EFV treatment initiation. Relevant IRB/EC and HA approvals will be secured prior to initiating the study.

2.1.1. Nested Case-Control Study Design

A nested case-control study will be conducted to evaluate the effects of ARV treatment adherence and pill intake with food on the risk of virologic failure with RPV. Information on food intake associated with taking RPV and ARV treatment adherence during the last 7 days will be collected retrospectively through a self-reported questionnaire in a smaller sample of RPV-treated patients nested within the DUS. Patients will be informed that their responses are confidential and have no consequences for their treatment. Cases for the case-control study will comprise all RPV-treated patients who experience virologic failure. For each case, four control patients without virologic failure will be chosen using incidence density sampling from the defined cohort of RPV-treated patients in the DUS. Incidence density sampling involves matching each case to a sample of those who are at risk at the time of case occurrence. This sampling method has been found to result in an unbiased estimate of the incidence rate ratio. The control patients will be matched on potential confounders for virologic failure, eg. age, sex, weight or body mass index (BMI), ethnicity, CD4 cell count, pre-treatment viral load, route of HIV infection, co-infection with hepatitis B/C, HIV treatment status (naïve/experienced), and depression. Risk of virologic failure associated with adherence to ARV treatment and dietary instructions will be quantified.

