The DUS will identify a minimum of 600 patients newly initiating RPV-containing regimens and 600 patients newly initiating EFV-containing regimens and captured in one or more of the HIV cohorts currently established in Europe. Exposure to RPV-containing regimens will be measured by the presence of prescription records for the fixed dose combination (FDC) of RPV with emtricitabine/tenofovir (TRUVADA TM (Gilead)) or single agent tablets of RPV among the patient data. Exposure to EFV will be measured by the prescription records for the available formulations of EFV in patient data. Information on drug use, including dispensing date, dose prescribed, quantity dispensed and the length of drug supply, will also be captured from the prescription records in the cohort database. The sample size targets will produce an error rate of no more than 5% for the proportions estimated. A minimum of 600 RPV-treated patients will be included in the DUS to assess the proportion of appropriate use of RPV-containing regimens. The study period will start at the date of market availability of RPV-containing products in the participating counties and will end when in total 600 patients from each treatment group have been included in the study and followed for 12 months, until virologic failure, or lost to follow-up, whichever occurs first.

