Given the recognized limitations of assessing food intake and treatment adherence in large observational studies conducted over several months, the feasibility of collecting food intake and treatment adherence data within the cohorts will be further explored. Currently, the HIV cohorts do not routinely collect data on ARV treatment adherence or pill intake with food. Optimally, HIV cohort data collection protocols will be modified for all RPV-treated patients to facilitate data collection on both ARV treatment adherence and pill intake with food at each patient visit. Under this scenario these measures will be added to the analysis described above. A nested case-control study will be conducted to address the CHMP's concerns on the effects of food intake on virologic failure among patient treated with RPV, while also evaluating ARV treatment adherence. The objective of the nested case-control analysis is to quantify the risk of virologic failure associated with adherence to ARV treatment and dietary instructions. Patients who experience virologic failure while under observation in the DUS will be selected into the study as cases. Patients who do not experience virologic failure while under observation and have similar experience with known confounders for virologic failure will be matched to cases using the incidence-density sampling method. This subgroup of patients from the DUS will be contacted and have their ARV treatment adherence and pill intake with food assessed through a one-time questionnaire assessing both adherence parameters over the past seven days. The methodology for the nested case-control study is provided in parallel with the DUS in this protocol.

ABBREVIATIONS

AACTG	Adult AIDS Clinical Trials Group
ARCA	Antiretroviral Resistance Cohort Analysis database
ARV	antiretroviral
BMI	body mass index
CHIC	Collaborative HIV cohort
CHMP	The Committee for Medicinal Products for Human Use
CI	confidence interval
CoRIS	Cohort of Spanish AIDS Research Network
DUS	Drug Utilization Study
EFV	efavirenz
FDC	Fixed dose combination
FTC	emtricitabine
FHDH	French Hospital Database on HIV
GPP	Good Pharmacoepidemiology Practice
HAART	highly active antiretroviral therapy
HIV-1	human immunodeficiency virus type 1
IRB	Institutional Review Board
J&JPRD	Johnson & Johnson Pharmaceutical Research and Development LLC.
MAR	missing at random
MCAR	missing completely at random
MNAR	missing not at random
M-PEMS	Modified Prescription Event Monitoring Study

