Exposure to RPV will be determined by the presence of prescription records for the FDC of FTC/RPV/TDF or single agent of RPV among patient data. Relevant drug codes will be used to identify RPV-containing regimens in the HIV cohorts. The baseline date for exposure follow-up (index date) for a patient within a given treatment group will be defined by first prescription of RPV or EFV-containing regimens. Duration of exposure will be based on dispense date and days of supply for each dispensed prescription. Exposure to RPV or EFV-containing regimens will be considered discontinued if the prescription is not refilled within a specified interval of time (e.g. twice the days' supply) of the previous prescription. Switches from one drug to another will be captured and time on drug will be defined by the exposure periods. The total length of exposure to a given drug will be the time between start and stop periods of exposure to the same drug.

4.2.1.1. **Exposure Definition in Nested Case-Control Study**

For the nested case-control analysis, exposure will be based on 1) level of daily medication adherence, and 2) level of adherence to food recommendations. Cases and matched controls that are selected will be asked to retrospectively report via a questionnaire how often they took their HIV medication during a specified time period and how often RPV was taken with food. A single item querying the number of prescribed doses the participant had missed in a specified time period will be used, as follows:

"How many doses of your complete HIV regimen did you miss in the last 7 days?"

"For those days you missed, what component of your HIV regimen did you miss?" (If applicable)

"How often did you take RPV with food in the last 7 days?"

Since RPV dosing is once-daily, number of doses taken is equivalent to number of days the medication is taken. A 7-day recall period is proposed for this analysis as it has the advantage of including a weekend, during which adherence is often problematic. Further, DATE (6 September 2011) 20

longer recall periods (7-day vs. 1-3 day) may yield more useful data for once-daily ART dosing since there are too few dosing times in a very brief recall period to capture variations in adherence behaviors (Simoni, 2006).

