5. STUDY LIMITATIONS

The proposed study is based on analysis of medical and prescription records from databases maintained by HIV cohorts in Europe. The following limitations should be considered:

There is potential misclassification of the diagnosis or the outcomes of interest.

Attribution of loss of virologic control to failure to follow RPV-containing products' SmPC may not be feasible given the multiple factors and dynamics salient to virologic control

Measurement of adherence to treatment regimens are difficult to assess with reliability beyond prescription refills. Reasons for switch of ARV treatment may be captured inconsistently across the HIV cohorts. Adverse events during the course of RPV or EFV-treatment will be described in aggregate; it is not possible or appropriate to assess the causality of individual cases.

Daily measurement of patient food intake with RPV-containing regimens is highly problematic in any study given the time required to measure diet consistently and accurately over the course of the study period. Associations between patient diet measurement and loss of virologic control are likely highly unreliable given misclassification of diet and consistent measurement of dietary intake. Furthermore, a thorough measurement using complicated instruments of the patient's dietary intake may result in changes in dietary behavior to an extent that the behavior becomes unrepresentative of true intake in the 'real world' setting.

Self-report of treatment adherence is susceptible to recall bias and social desirability bias. Self-reported measures reflect only short-term or average adherence and may often overestimate it, particularly when queried retrospectively.

DUS include bias related to the observational nature of the data and potential lack of data due to loss to follow-up or essential data not collected as routine fields. These studies are also subject to real-world prescribing practices that may not provide sufficient patient numbers to meet study goals of ascertainment within a reasonable timeframe. The feasibility evaluation and design assessment of the study are intended to better understand and adjust for these limitations as well as to estimate the probability to meet study goals of ascertainment within a reasonable timeframe.

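### The nested case-control study reads adherence and food intake in a week that follows failure for cases and is not tied to the matched time for controls, so its odds ratios may be differentially biased

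*Protocol*

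**What the plan says.** The order of events is set in several places.

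- **Selection of cases.** The Synopsis states: "Patients who experience virologic failure while under observation in the DUS will be selected into the study as cases". Section 4.2.3 uses the same failure definition for cases, and Section 4.2.5 ends a patient's follow-up at failure.
- **Questioning.** Section 2.1.1 provides that food intake and "ARV treatment adherence during the last 7 days will be collected retrospectively through a self-reported questionnaire". Section 4.2.1.1 states: "Cases and matched controls that are selected will be asked to retrospectively report via a questionnaire". The Synopsis says that patients are contacted and have treatment adherence and "pill intake with food assessed through a one-time questionnaire assessing both adherence parameters over the past seven days".
- **Item wording.** Section 4.2.1.1 prints the items. The food item is "How often did you take RPV with food in the last 7 days", and the missed-dose item uses the same window. No section ties the window to the date of failure or to the matched time.
- **Controls.** Section 2.1.1 draws four per case by incidence density sampling from patients at risk when the case occurs, and justifies this as giving an unbiased incidence rate ratio.
- **Classification.** Section 4.2.1.1 calls a patient adherent above 80%. Food adherence is the number of doses taken with food divided by doses taken.
- **Refill data.** The Synopsis says that drug-use information, "including dispensing date, dose prescribed, quantity dispensed and the length of drug supply, will also be captured". Section 5 concedes: "Measurement of adherence to treatment regimens are difficult to assess with reliability beyond prescription refills".

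Collection of both measures at every visit is raised in the Synopsis and Section 1.1, but only as an option whose feasibility is still to be assessed.

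**The concern.** The nested study has one primary objective (Section 1.3.1): to quantify the risk of failure associated with adherence and, separately, with food intake. That needs exposure from before the failure. As written, a case's exposure is read after failure has been observed and after that patient's own follow-up has closed. Where failure needs two consecutive values above 500 copies/ml, the questionnaire is later still relative to loss of control.

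Incidence density sampling gives an unbiased rate ratio when exposure is read as of the risk-set time. Here controls are chosen at that time but questioned about a later week, so the stated justification does not carry over to the exposure as measured.

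Learning of a failure may change behaviour or regimen in cases and not in controls. The resulting error would be differential, and neither more cases nor closer matching would remove it. What is at stake is the answer to the CHMP's question about food intake and RPV failure. A week that was never asked about cannot be recovered in the analysis.

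**Working it through.** **1. The plan's own figures.** Section 4.1.2 assumes a two-sided alpha of 0.05, four controls per case and 50% exposed. With p0 = 0.5 and p1 = p0 × OR / (1 + p0 × (OR − 1)), the two-proportion approximation is

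power = Φ[(|p1 − p0| − 1.96 × SE0) / SE1],

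with SE0 pooled and SE1 unpooled.

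- OR 3.0, 40 cases, 160 controls: p1 = 1.5/2 = 0.75. The pooled proportion is (30 + 80)/200 = 0.55. SE0 = √(0.2475 × 0.03125) = 0.0879 and SE1 = √(0.1875/40 + 0.25/160) = 0.0791. Power = 0.837; Table 1 gives 0.828.
- OR 2.0, 90 cases, 360 controls: p1 = 1/1.5 = 0.667. The same formula gives 0.820; Table 1 gives 0.816.

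The table is arithmetically sound. It takes the measured exposure to be the one that preceded failure.

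**2. Time order.** For cases the sequence is failure, selection, contact, then a question about the preceding seven days. The window would precede failure only if the questionnaire were answered on the day of the failing sample, and nothing provides for that.

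**3. How much rests on one week.** Dosing is once daily. One missed dose gives 6/7 = 85.7% (adherent); two give 5/7 = 71.4% (nonadherent). With no RPV doses taken, the food ratio has a zero denominator.

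**4. Illustration of bias.** The prevalences and the fractions changing behaviour are assumptions; the protocol gives none of them. Controls are held fixed. Before failure, 40% of cases and 15% of controls are nonadherent:

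OR = (0.40/0.60)/(0.15/0.85) = 3.78.

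If a fraction f of nonadherent cases has become adherent by the questionnaire, case nonadherence is 0.40 × (1 − f):

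| f | Case nonadherence | Observed OR |
|---|---|---|
| 0.25 | 0.30 | 2.43 |
| 0.50 | 0.20 | 1.42 |
| 0.75 | 0.10 | 0.63 |

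In the other direction, if 25% of adherent cases become nonadherent after failure, case nonadherence is 0.40 + 0.25 × 0.60 = 0.55 and the observed OR is (0.55/0.45)/(0.15/0.85) = 6.93.

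**5. The same with the protocol's 50% prevalence and target odds ratios.**

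- True OR 3.0 (p1 = 0.75): f = 0.25 gives 0.5625/0.4375 = 1.29, and f = 1/3 gives 1.0.
- True OR 2.0 (p1 = 0.667): f = 0.25 gives 0.50/0.50 = 1.0.

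**The case against.** **Recent behaviour may be a fair proxy.** If patients behave after failure as they did before, the last seven days stand in for the earlier week. A reader might infer that the odds ratios cannot answer the question at all. The protocol does not support that, because it gives neither the lag to contact nor the frequency of change. What stands is that the proxy assumption is neither stated nor tested.

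**The magnitude is illustrative.** The 40% and 15% are not the protocol's figures, and the drop to 0.63 needs three quarters of nonadherent cases to have changed. This is correct. The numbers show sensitivity and do not estimate the bias.

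**Loss of cases is not stated.** A reader might infer that patients who have left RPV are dropped. No section says so, and the missed-dose item asks about the complete HIV regimen, so it can still be answered after a switch (though it then describes the new regimen). Only the food ratio becomes undefined, and how many cases this would affect is unknown.

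**The protocol already admits weaknesses.** Section 5 names recall bias, social desirability bias, short-term measurement and unreliable diet data. It does not name exposure measured after the outcome. Per-visit collection would give pre-failure exposure if carried out, but it is conditional and is not the nested study's exposure definition.

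**Refill data have limits.** Section 1.1 lists refill monitoring among methods limited by cost and labour, the cohorts are not yet chosen (Section 3.1.3), and refills say nothing about food. This stands, so refills should supplement the questionnaire and not replace it.

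**Conclusion.** The point holds for the nested case-control component. Exposure in cases is measured after failure, and exposure in controls is not measured at the matched time. If behaviour or regimen changes after failure, both odds ratios are differentially biased, in a direction that the protocol gives no means of judging. With the protocol's own planning inputs, correction by a quarter of nonadherent cases would remove a true odds ratio of 2.0, and by a third a true odds ratio of 3.0. With the other assumed inputs, 3.8 becomes anything from 0.6 to 6.9. All of this depends on assumed fractions and unchanged controls. If nobody changes behaviour, this bias is absent.

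A reader might extend the criticism to the whole study. The documents do not support that: the objectives on use according to the SmPC, treatment-emergent resistance mutations and virologic failure rates do not use the questionnaire.

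**What to change.** 1. **Index date.** For a case, use the date of the sample on which the failure definition in Section 4.2.2 is met. Where that definition needs two consecutive values, end the exposure window at the first of the two qualifying on-treatment samples. Give matched controls the same time since RPV start. The first viral load above 500 copies/ml would not serve: for patients above 500 at baseline it is the baseline sample, and values before month 6 are not failure under Section 4.2.2.
2. **Questionnaire.** Word both items to the seven days before the index sample (the first of the two where two values are needed), or the last seven days on RPV if it was stopped earlier. Record the lag from index date to completion, and run a sensitivity analysis limited to short lags.
3. **Pre-failure measures.** Add refill-based medication adherence over a fixed window ending where the exposure window ends, from the dispensing date and days' supply already captured, in cohorts that hold the data. Where adherence and food are collected at visits, use the last visit before the index date.
4. **Limitations.** State in Section 5 that the questionnaire is answered after the outcome.

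The cost is protocol and questionnaire wording, one recorded lag and one derived refill variable. The drawbacks are longer recall, especially for the food item, and refill data that may be incomplete in some cohorts and cannot measure food intake.

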2.2. Study Design Rationale

A DUS design using existing HIV cohorts was chosen to assess proper prescribing and effectiveness of RPV-containing products in routine clinical practice in Europe and to provide the greatest access to HIV prescribers. HIV cohorts operating in Europe and using electronic medical record-based databases have proven to be an important resource for post-marketing observational studies in HIV. These studies are generally not subject to additional informed consent and may be completed expeditiously.

An important strength of these cohorts relevant to the proposed DUS is their ability to evaluate conditions under which HIV drugs are prescribed in large numbers of patients. Data from these cohorts are useful in evaluating treatment patterns and appropriateness of treatment. The design was also chosen due to the robust patient numbers available within

the HIV cohorts in Europe that capture the experience of patients with HIV. Multiple HIV cohorts will be evaluated for inclusion in the DUS to meet the study objectives and sample size requirement of 600 patients exposed to RPV-containing regimens and 600 patients exposed to EFV-containing regimens.

The proposed HIV cohorts have been established in Europe specifically to facilitate research in HIV infected patients. Data salient to meeting the CHMP request are available within the HIV cohorts and do not require additional data collection or interaction with physicians or patients with the exception of robust food intake and adherence measures. It is important to note that one of the reasons these cohorts were established was because traditional resources for patient identification were insufficient in identifying HIV infected patients due to HIV infected patients seeking treatment outside of payer systems and from health care providers other than general practitioners.

European HIV cohorts capture care as given and are generalizable to the population likely to be exposed to RPV-containing regimens. The proposed design does not interfere with the physician's decision regarding what to prescribe for the individual patient. Patients receive the drug in everyday practice and are not a highly selected group of patients who may not be representative of the 'real-world' population. The use of multiple cohorts located in several different countries increases the generalizability of the observed rates of use by physicians. The major strength of using the HIV cohorts for a DUS is the protocols for data collection have been specifically designed for HIV research (www.hicdep.com). Data are systematically collected on all clinical aspects salient to HIV care. These data include laboratory variables for HIV viral load, CD4+ counts, drug resistance information, concomitant medications, adverse events, and detailed information on HIV treatment. Additionally, patients are followed in the cohort until death or loss to follow-up from the cohort. Data are collected independent of the proposed DUS and are not subject to physician recall or potential biases involving selfreported drug prescribing or patient management. These data are collected longitudinally and in a time-dependent manner so that variation in time-dependent variables can be assessed. This is particularly important when considering the outcome of virologic failure and potential factors contributing to loss of virologic control. Finally, these data are collected electronically and do not place additional burden on the treating physician or patient.

Additionally, a comparator group of EFV-treated patients will be included in this study to provide contemporary context to utilization and outcomes observed within the RPVtreated group. The EFV-treated group will provide insight into patient characteristics DATE (6 September 2011)

likely to influence health-care providers to channel patients to EFV-containing regimens or to RPV-containing regimens. Additionally, the EFV treatment group will provide a better understanding of the observed rates of virologic failure and prescribing factors observed within the RPV-treated group.

